This design is a two-armed clinical trial, with replicate measures at three time points: baseline, three, and six months. Since subjects are randomized to either WL-Control or WL-Protein arm, and the groups are presumed equal at baseline, the analysis is straightforward. Following the Good Clinical Practice Guidelines for the analysis of a clinical trial, we will employ mixed models, analyze under an Intent to Treat (ITT) criteria, and control for baseline and assess the impact of Time, Treatment Group and the interaction of these variables on the outcomes. Relative to the usual repeated measures designs, mixed models have several advantages: 1) missing values present no particular difficulties in estimation and the estimates are unbiased as long as the set of variables leading to MAR are estimated, 2) the usual assumption of conditional independence (compound symmetry) used in standard repeated measures need not be made, and 3) the actual times of measurement need not be equivalent across subjects. Controlling for the individual baseline values for the particular outcomes, the trajectories over time and differences in those trajectories will be assessed. Following the statistical principles section from the International Conference on Harmonization, we will select covariates (e.g., age, race, number of comorbidities) for the primary models a priori, but we also will conduct auxiliary sensitivity analyses that evaluate whether potential group imbalances bias the treatment effect estimate. These analyses will be performed using conventional testing for confounding. We note that we have listed numerous measures to be analyzed as outcomes, but have listed only 1 primary outcome (physical function, Aim 1).

For any particular outcome, the general form of the model will be:

$$Y_{it} = \beta_0 + \beta_1(\text{group}) + \beta_2(\text{time}_t) + \beta_3(\text{group} * \text{time}_t) + \beta_4(\text{covariates}) + \epsilon_{it}$$

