Where i is an indicator of person, and time is defined as $t=1, 2$ (measuring month 3, and 6), and the β 's are regression coefficients connecting the predictors to the outcome. For brevity, we list β_4 as a vector of K regression coefficients linking the K covariates to the outcome. As defined, the overall test of the intervention effect will be the joint effect of group and group*time on 2 df (β_1 and β_2) assessing an overall effect of group, and if this group effect is constant over time. If significant, follow-up tests will assess where group differences lie. In particular, we note that if the time by group interaction is rejected, we will test if the groups differ at the end of 6 months (a test of effect at the completion of the intervention). We will carefully examine model assumptions, including the distribution of model residuals, additively, linearity, and influential observations, and will, if necessary, re-parameterize the models or transform the outcomes accordingly.

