Primary outcome data collected during the trial will be analyzed for differences due to race. Using the same analytic strategy listed in the analysis of Aims 1 and 2, race (B/W) will be included into the analytic structure for the physical function (SPPB) outcome, first as a main effect (mediating), and secondly, as an interaction (moderating) with group. If the physical function change outcome is normally distributed, we will employ, 2-way ANCOVA, with race and group serving as factors, and controlling for baseline physical function. While our working hypotheses are directional, our tests will be two-tailed. If physical function is not distributed approximately normal, we will attempt to assess the outcome using appropriate transformations, or bootstrapping simulations⁶¹. We are aware race and compliance may be partially confounded. As a final sensitivity analysis, we will assess if any observed relationships are mediated by compliance with the protocol. Next secondary outcomes data collected will be used to test the hypotheses about racial differences. Preliminarily, we will assess if the distributional assumptions of the outcomes of the ANCOVA model are met. If not, we will attempt to delimit an appropriate transformation, or employ bootstrapping. To assess the racial effects, the change of these outcomes by intervention group and race will be assessed, controlling for the baseline levels. Both the interactive (with group) and the main effects of race and group will be assessed. In addition, we will assess if the race effects are mediated by compliance. We will not control for the Type-I error rate inherent in multiple testing of multiple outcomes. Rather, for any relationship declared statistically significant, the reader will be alerted to the preliminary nature of the findings, the multiple testing issues and the requirement for replication. The results of these analyses will provide invaluable information regarding the process and functional forms and, potentially, the causal pathways of the intervention process. For example, one important analysis will enter 'level of compliance to the intervention' into the analysis, allowing for a 'per protocol' analysis of the results.

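### Aim 3 promises the Aims 1 and 2 mixed model but specifies a two-way ANCOVA on a single change score, with no end visit and no missing-data rule

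*Combined protocol and SAP*

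**What the plan says.** Analysis Plan for the parent protocol (Aims 1 and 2): "we will employ mixed models, analyze under an Intent to Treat (ITT) criteria, and control for baseline". The repeated responses are "measuring month 3, and 6". One stated reason for this choice is that "missing values present no particular difficulties in estimation", with unbiasedness claimed under missing at random.

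Analysis Plan (Aim 3) opens with "Using the same analytic strategy listed in the analysis of Aims 1 and 2" and adds race as a main effect and as an interaction with diet group. The next sentence changes the method. "If the physical function change outcome is normally distributed", then "we will employ, 2-way ANCOVA, with race and group serving as factors, and controlling for baseline physical function". If the change is not normal, "we will attempt to assess the outcome using appropriate transformations, or bootstrapping simulations". For the secondary outcomes, "the change of these outcomes by intervention group and race will be assessed, controlling for the baseline levels".

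The Aim 3 text has no time term, names no end visit for the change and gives no rule for missing visits. The Aims 2 and 3 analysis in the supplemental protocol keeps the mixed model.

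Two facts in the Design section bear on this. About 160 men are to be enrolled, with 30% dropout, to reach 112 completers. Men enrolled after 10/1/2023 are followed for 3 months only.

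**The concern.** Two adjacent sentences name different methods. The first points to a longitudinal model that uses a man's month-3 value when month 6 is absent. The second points to a model with one record per man, which can use him only if the chosen change exists. With no missing visits the two would give essentially the same month-6 contrast, so the conflict matters through missing data. This trial expects a good deal of missing data, some of it by design.

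At stake are the race and race-by-diet estimates. They could come from a different set of men, under a different missing-data assumption, than the Aim 1 diet effect they are meant to elaborate. The race-by-diet interaction is also the contrast with the least precision to spare.

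**Working it through.** **1. The plan's own figures.**
- Enrolment: 112/(1 - 0.30) = 160, so 160 - 112 = 48 men are expected to drop out.
- Power Estimate section, with SD 1.7, 50 per arm, two-sided 0.05 and 80% power: (1.960 + 0.842) × 1.7 × √(2/50) = 0.953 units. With the t distribution it is 0.962 units, or 0.566 SD. Both stated values, 0.96 and 0.57, reproduce. No power figure is given for Aim 3.
- The documents also give 84 per arm and, for power, 100 in total. I use 160 and 112 because they carry the dropout assumption.

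**2. What the unnamed end visit could be.**
- Month 6: men who leave between months 3 and 6 lose their month-3 data, and all shortened-study men are out.
- Month 3: every month-6 value is unused.
- Each man's last visit: 3-month and 6-month changes are pooled. The Aims 1 and 2 plan itself expects change to be fast at first and then to flatten, so these are not the same quantity.

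**3. Precision under the month-6 reading.** With n2 = 112 men at month 6 and n1 dropouts who have month 3 only, the variance ratio (mixed model to ANCOVA) for the month-6 contrast is 1 - ρ² × n1/(n1 + n2). Here ρ is the month 3-6 correlation given baseline, since both models adjust for baseline. The share with month 3 and ρ are assumptions; the documents give neither.
- 50% of 48, n1 = 24, ρ = 0.5: 1 - 0.25 × 24/136 = 0.956. Effective size 112/0.956 = 117. SE ratio √0.956 = 0.978.
- 75% of 48, n1 = 36, ρ = 0.7: 1 - 0.49 × 36/148 = 0.881. Effective size 112/0.881 = 127. SE ratio √0.881 = 0.939.

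If 0.5-0.7 were raw correlations and baseline correlated 0.5 with each visit (a further assumption), then ρ = (0.5 - 0.25)/0.75 = 0.33 to (0.7 - 0.25)/0.75 = 0.60. The ratios become 0.980 and 0.912, a gain of about 2-10% in information. Over a wider range (25-100% with month 3, ρ = 0.5-0.8) the effective size is about 115 to 139, and the ANCOVA standard error is 1-11% larger.

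These figures treat all 160 men as 6-month participants. If shortened-study men count among the 112 completers, a month-6 ANCOVA uses fewer than 112. Their number is not given.

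**4. The interaction.** With 112 men in four equal cells of 28, the 80%-power detectable race-by-diet interaction is 2.802 × 1.7 × √(4/28) = 1.80 units. The whole diet effect in the pilot was 2.4 - 0.9 = 1.5. Applying the SE ratios from step 3 gives 1.80 × 0.978 = 1.76 and 1.80 × 0.939 = 1.69, so the mixed model helps but does not cure low power.

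**5. Bias.** In a simulation of 2,000 replicates, with 160 men, about 30% missing month 6 and month 3 always observed, dropout in one race-by-arm cell depended on the month-3 value (log-odds 0.5 or 1.0 per SD, ρ 0.5 or 0.7). The complete-case interaction was biased by 0.13 to 0.34 units. With month 3 in the model the bias was at most 0.01 in absolute value. When dropout did not depend on month 3, neither analysis showed bias beyond simulation error. The dropout mechanism is assumed.

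**The case against.** The ANCOVA sentence can be read as describing only the factor layout, with the mixed model still in force. The opening of the paragraph supports that reading. Against it, the sentence that follows makes the model depend on the normality of a change outcome, the fallback is transformation or bootstrap rather than a repeated-measures model, and the secondary outcomes are also framed as change. The text does not settle the matter, and that ambiguity is itself a reason to revise it.

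A reader might infer that the plan definitely excludes 48 men. It does not say so: no end visit and no complete-case rule are stated, and the exclusion follows only under the month-6 reading. A reader might also infer that dropout is expected to differ by race. The Aim 3 text says only that race and compliance may be partly confounded; compliance is not dropout, and nowhere is dropout predicted by race. The planned compliance-mediation and per-protocol analyses answer a different question and do not handle missing visits.

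It is also fair that baseline-adjusted ANCOVA is a valid standard method, that Aim 3 is labelled exploratory, that its findings are to be presented as preliminary and needing replication, and that the Aim 1 analysis is unaffected. All of this limits the priority. None of it reconciles the two sentences.

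**Conclusion.** The conflict between the promised and the specified method is real, and the Aim 3 text leaves the end visit and the handling of missing visits open. Under the natural month-6 reading the cost in precision is small: 117-127 effective men against 112, or a standard error about 2-6% smaller with the mixed model, and less if the correlation given baseline is lower. These figures rest on an assumed share of dropouts with month 3 and an assumed correlation. Protection against bias could matter more, but only if dropout depends on month-3 response, which the documents neither state nor exclude. Men with no post-baseline visit are lost under either model. This is a modest-priority change to an exploratory aim.

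**What to change.** For SPPB and every repeatedly measured secondary outcome, make the baseline-adjusted mixed model of Aims 1 and 2, with race, race*group, race*time and race*group*time added, the Aim 3 analysis. Report the diet effect within each race and their difference at month 6, with 95% confidence intervals. Keep the two-way ANCOVA as a sensitivity analysis at a named visit, and state how missing visits are handled there.

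The cost is a few sentences and extra terms in a model that is already planned. There is one small downside to state. Letting the month-3 data of shortened-study men inform the month-6 contrast assumes that their later course would match that of the 6-month men, although their weight-loss target differs (5-10% rather than 10%). Add a cohort term, or a sensitivity analysis without these men. The three-way term is also estimated from only about 28 completers per race-by-arm cell, so the intervals will be wide and should be presented as such.

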In addition to the impact of the intervention on the secondary outcomes, we will assess mediation of the group effect on the primary outcome by demographic, comorbid and adherence variables. Subjects may differ in their process of change depending on baseline demographic and functional status values. Second, we will assess the functional form of the change over time, by looking at non-linear functions of change. For example, change in function and performance is likely to be non-linear, initially changing quickly and leveling at points distal from baseline. It would be important to note if this change differed by group. Finally, we will assess whether the trajectories of change, irrespective of group assignment, are similar for individuals. In this application, we have listed several variables, which we expect to change as result of the intervention. We further hypothesize that all these variables will change in the same pattern. To test this hypothesis, across the range of outcome measures, we can look at overall change through the use of multivariate tests (Boc⁵⁹ or Anderson⁶⁰) for the singly measured functional items, and by assessment of correlated trajectories for those outcomes measured repeatedly. With appropriate weighting for number of observations per individuals, the correlation between individual trajectories can be assessed. A positive correlation between the trajectories for any two outcomes will indicate that the subjects changed similarly for the 2 outcomes, and will provide

additional support for the notion that the intervention had a generalized effect across the outcomes. Significant correlations would perhaps indicate mechanistic/causal linkage between variables over time, or, from a reliability standpoint, may indicate that the subsequent trial may want to employ summary measures aggregating across outcome measures, or, alternatively, employ multivariate tests across several outcomes to assess the group differences, reducing the chance of Type-I error inherent in the testing of multiple variables. We will not adjust for Type-I error rate for these secondary outcomes.

Analysis Plan (Aim 3):

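### A model with compliance entered as a covariate is called a per-protocol analysis, but its group coefficient is not the diet effect among men who followed their diet

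*Combined protocol and SAP*

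**What the plan says.** The Analysis Plan (Aim 3) closes with an example of how its analyses may throw light on process and, "potentially, the causal pathways of the intervention process". The example, which the plan calls an important one, is to bring compliance level into the analysis, "allowing for a 'per protocol' analysis of the results". The plan gives no compliance score, threshold or per-protocol population, and no method for handling confounding of compliance with outcome. The only confounding it admits concerns race: "We are aware race and compliance may be partially confounded".

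Three other places bear on the point.

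- **Analysis Plan for the parent protocol (Aims 1 and 2).** The mixed models will "analyze under an Intent to Treat (ITT) criteria". For covariates, "we will select covariates (e.g., age, race, number of comorbidities) for the primary models a priori". The examples are all baseline variables, and compliance is not among them.
- **Measures and Data Collection Points.** Adherence comes from diet records and food journals at 0, 3 and 6 months (0 and 3 months for the shortened study), so it is mostly observed after randomisation.
- **Study Interventions.** The arms have different targets (0.8 versus 1.4 g protein/kg/day) and different food supply. WL-Protein receives 21 weekly servings of 30 g, partly in order to raise compliance. WL-Control receives 7 weekly servings of 15 g.

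**The concern.** A per-protocol analysis normally means either a prespecified adherent subset or an estimate of the effect had everyone adhered. Adding compliance to a regression gives neither. It compares men in the two arms who have the same compliance score, and that comparison is no longer protected by randomisation.

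Two things can go wrong. First, if arm affects compliance and compliance shares an unmeasured cause with SPPB, men matched on compliance are not matched on that cause. Part of the cause's effect is then attributed to diet. Second, if compliance lies on the path from diet to SPPB, adjusting for it removes part of the real effect.

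The arms also ask for different behaviour, so an equal score need not mean the same thing in both. At stake is a secondary estimate that could be set beside the intention-to-treat result, or against it, under a label it has not earned.

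**Working it through.** **The plan's own figure.** The Power Estimate gives a pilot difference of 2.4 − 0.9 = 1.5, SD 1.7, total N = 100, two-sided α = 0.05.

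- Standard error with 50 per arm: 1.7 × √(2/50) = 0.34.
- Power at 1.5: Φ(1.5/0.34 − 1.96) = Φ(2.45) ≈ 99.3% (99.2% by t-test), against a stated value above 99%.
- Detectable difference at 80% power: (1.96 + 0.84) × 0.34 ≈ 0.95 (0.96 by t-test), against the stated 0.96.

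Both figures reproduce, so 0.96 is a fair yardstick.

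**Model for the bias.** Let G be arm (1 = WL-Protein). Let U be an unmeasured prognostic factor with variance 1, C be compliance scaled to SD 1 within arm, and Y be SPPB change with SD 1.7 within arm.

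- C = aG + rU + noise, where a is the arm difference in compliance, in SD units.
- Y = δG + 1.7rU + noise, where δ is the true diet effect. Compliance has no effect of its own here, which isolates the first mechanism.

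The within-arm slope of Y on C is cov(C, Y)/var(C) = r × 1.7r / 1 = 1.7r². Adjusting for C changes the group coefficient by −a × slope:

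**bias = −a × r² × 1.7**

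**Inputs.** The SD of 1.7 is the plan's. The 56 per arm is half of the 112 completers in the Design section. The values of a and r are assumptions, since the documents give neither: |a| = 0.5 to 1 and r = 0.3 to 0.7.

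| \|a\| | r | Size of bias | Rejection rate, δ = 0 | Adjusted estimate, δ = 0.96, protein arm more compliant | Adjusted estimate, δ = 0.96, protein arm less compliant |
|---|---|---|---|---|---|
| 0.5 | 0.3 | 0.08 | 4–5% | 0.88 | 1.04 |
| 0.5 | 0.5 | 0.21 | 9% | 0.75 | 1.17 |
| 0.5 | 0.7 | 0.42 | 29–32% | 0.54 | 1.38 |
| 1 | 0.3 | 0.15 | 6% | 0.81 | 1.11 |
| 1 | 0.5 | 0.425 | 23% | 0.535 | 1.385 |
| 1 | 0.7 | 0.83 | 73–76% | 0.13 | 1.79 |

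Bias and estimates come from the formula. For example, 0.5 × 0.09 × 1.7 = 0.08 and 1 × 0.49 × 1.7 = 0.83. Rejection rates come from least-squares simulation, 1,500 trials per scenario and 56 per arm, and the simulated means agreed with the formula. Unadjusted, the contrast was unbiased and rejected a true null 4% to 6% of the time. With δ = 0.96, unadjusted power was about 84% to 86%. Adjusted power with the protein arm more compliant ran from 76% down to 7%.

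**Relative size.** 0.08/0.96 ≈ 8% and 0.83/0.96 ≈ 86% of the detectable difference. The formula contains no sample size: at 84 per arm the simulated bias was the same, and null rejection reached 90% in the strongest scenario.

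**The case against.** The strongest reply is that little depends on this analysis. It is offered as an example at the end of an aim that the Specific Aims label exploratory, while the primary comparison is intention-to-treat with covariates chosen in advance. The plan also says significant findings will be presented as preliminary and needing replication. That stands as a limit on the consequences. The warning does not name this bias, however, and replication would not remove it, because it does not shrink with sample size.

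Second, the bias is conditional. The protocol says both arms get equal attention and support, so compliance may turn out balanced. Control for baseline SPPB, which the plan intends and the illustration omits, could absorb part of the shared prognosis. Both points stand, which is why a range is shown. Nothing in the plan secures either condition, and the unequal food supply makes imbalance plausible.

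Third, the text does not say whether compliance enters as a main effect, an interaction or a subset, or which coefficient will be reported. A covariate is the most natural reading, but the wording is open. That is itself a reason to specify the analysis.

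A reader might also extend the criticism to the sentence "As a final sensitivity analysis, we will assess if any observed relationships are mediated by compliance with the protocol", or to the statement in the Aims 1 and 2 plan that "we will assess mediation of the group effect on the primary outcome by demographic, comorbid and adherence variables". The documents do not support that. These are mediation analyses, not presented as per protocol, and conditioning on a post-baseline variable is inherent in mediation. The first also follows directly on the remark about race, which is not randomised. Both deserve a no-confounding caveat, but neither is the mislabelled analysis.

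**Conclusion.** The point holds for the compliance-covariate model and its label. As written, the group coefficient from that model loses the protection of randomisation and does not estimate the effect among men who followed their diet. No other section corrects this.

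The size is unknown. Over the assumed range the bias is about 0.08 to 0.83 SPPB units, in either direction: upward if the protein arm complies less, downward if it complies more. It is zero if compliance is balanced between arms or unrelated to prognosis. These figures rest on a single shared factor, equally correlated with compliance and outcome, on no causal effect of compliance, and on no baseline adjustment. If compliance does mediate the diet effect, adjusting for it also removes part of that effect.

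A reader might infer that the trial's main diet comparison is compromised, or that a biased diet effect is certain to be reported. The documents support neither. The Aims 1 and 2 analysis is intention-to-treat and unaffected, the bias depends on two conditions that the documents do not settle, and the plan offers insight into causal pathways only as a possibility.

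**What to change.** In the Analysis Plan (Aim 3), remove the per-protocol label from the model that includes compliance. Report that model as descriptive only, and state that its group coefficient will not be interpreted as a diet effect. This costs almost nothing.

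If a per-protocol estimate is wanted, then before analysis:

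- define compliance separately for each arm, using the diet records and protein checklists already collected;
- define the per-protocol set;
- weight for baseline predictors of adherence, including baseline SPPB;
- state that the estimate assumes no unmeasured confounding of adherence and outcome.

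No new data are needed. The cost is a little more analysis work and a secondary estimate that is less precise and depends on assumptions. Weighting on baseline variables cannot remove bias from a trait that was not measured, so the last item must appear wherever the estimate is reported.

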Setting: Screening, baseline, outcome testing and intervention meetings will be conducted at the Sarah W. Stedman Center for Nutritional Studies on the Center for Living Research and Wellness campus at Duke University. Diet and exercise classes will be offered virtually via WebEx or in person at the Center for Living campus. Anthropometrics, functions tests, and blood collection will take place in the Clinical Research Unit there or may be conducted virtually if needed. The Isokinetic knee extension peak torque testing and BodPod body composition measurements will be done in the Sports Sciences Institute, which is adjacent to the Stedman Building. The thigh CT scans will be conducted in Radiology at the Veterans Affairs Medical Center in Durham.

We will enroll participants until we reach a total of 112 study completers. We anticipate enrolling approximately 160, allowing for a 30% dropout rate.

Study Arms:

- **Arm 1: WL-Control (n=56 completers)**
10%* WL diet with 0.8 g protein/kg body wt/day
- **Arm 2: WL-Pro (n=56 completers)**
10%* WL diet 1.4 g protein/kg body wt/day; \geq 30g high quality protein per meal

**Participants enrolled after 10/1/2023 will participate in a shortened study period of 3 months, with only 0 and 3 month assessments for most measures, as noted in the added footnotes below. Their weight loss prescription will be targeted to an expectation of at least 5-10% loss of body weight.*

Measurements:

After the participant has been consented and HIPAA Authorization forms have been signed, screening and baseline assessments will be conducted:

Screening process:

Screening Visit : Consent; confirm BMI ≥ 30 kg/m², confirmed SPPB score of 4-11, confirmed fasting plasma glucose ≥ 95 and < 126 mg/Dl or A1c between 5.7-6.4 (will be confirmed with LapCorp results), and confirmed Mini-Cog score ≥ 3 (if less than 3, confirm participant can conduct all ADLs).

Upon the completion of all baseline assessments (see below), the study biostatistician will then use permuted-block randomization to assign participants to WL-Control or WL-Protein groups. The following variables will be blocked in this order: 1) Race (white versus non-white, 2) Couple/Single status. An equal number of participants will be randomized across the two arms to end up with N=84 (42 black and 42 white) in each arm.

Measures and Data Collection Points

Primary outcome: Physical function (SPPB)

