Power Estimate: The sample size of $n = 84$ per group is based directly on our findings in the MEASUR-UP study, which used the same diet treatments, study population, and primary outcome as in the present Aim 1. In MEASUR-UP, the SPPB score for WL-Pro changed by +2.4 units over the course of the study, while the WL-Control group experienced an increase of +0.9 units. The pooled standard deviation of these changes is 1.7. Thus, the MEASUR-UP study observed a standardized difference of $0.88 = (2.4 - 0.9)/1.7$. Differences of this magnitude have been labeled as 'large' in the power analysis literature. Assuming equivalent effect sizes observed in the MEASUR-UP study, an overall sample size of 100 (evenly divided between groups), and a Type-I error rate of 0.05 (two tailed), the power of our design is greater than 99% to declare significance for the effect size observed in the pilot. At 80% power, this design is powered to detect a difference in change scores in the SPPB of 0.96, or a standardized difference of 0.57.

Analysis Plan for the supplemental protocol:

Aim 1: Feasibility-Recruitment capability: Proportion of participants recruited will be calculated as the number of participants deemed potentially eligible and contacted for enrollment divided by the total number of

participants enrolled. Feasibility of recruitment hypothesis: ≥35% of participants approached for recruitment will agree to participate

Feasibility-Retention: Retention proportion retention will be computed by dividing the number of retained subjects at the end of the intervention by the total number randomized into the study.

Retention hypothesis: ≥80% of participants will remain in the study for the duration of the trial

We will calculate the rate of retention and its respective confidence intervals overall and by group. While non-powerful, we will assess if these rates differ by chi-square test of proportion and Poisson regression respectively. In a series of sensitivity tests, we will assess if retention overall was impacted by demographic and high risk variables.

Feasibility-Intervention Tools: Records of intervention tools and time spent to administer them will be used for post-study analysis of intervention tool effectiveness.

Acceptability-Satisfaction: participant satisfaction of intervention delivery, overall experience, and outcomes will be assessed using a Likert scale and open-ended questions.

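### The power figures rest on a total of 100 men, a number planned nowhere; the protocol elsewhere plans 112 completers from about 160 enrolled, and also 84 randomised per arm (168)

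*Combined protocol and SAP*

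**What the plan says.** The Power Estimate paragraph (Data Analysis and Statistical Considerations) begins: "The sample size of $n = 84$ per group is based directly on our findings in the MEASUR-UP study". It takes changes of +2.4 and +0.9 SPPB points and a pooled SD of 1.7 from that pilot. It then assumes "an overall sample size of 100 (evenly divided between groups") and a two-tailed Type-I error rate of 0.05. It reports power above 99% for the pilot effect and, at 80% power, that "this design is powered to detect a difference in change scores in the SPPB of 0.96, or a standardized difference of 0.57".

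The Design section, under Setting, gives the recruitment rule: "We will enroll participants until we reach a total of 112 study completers". It continues: "We anticipate enrolling approximately 160, allowing for a 30% dropout rate". Study Arms lists 56 completers in each arm. The randomisation paragraph under Screening process says that an equal number of participants "will be randomized across the two arms to end up with N=84 (42 black and 42 white) in each arm".

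Two further statements bear on what the figures mean. The note to Study Arms places men enrolled after 10/1/2023 in a 3-month study "with only 0 and 3 month assessments for most measures". The Analysis Plan for the parent protocol (Aims 1 and 2) does not use a change-score t-test. It specifies mixed models that "control for baseline and assess the impact of Time, Treatment Group and the interaction of these variables on the outcomes", with the intervention effect tested jointly on 2 df.

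**The concern.** The Power Estimate is the only quantitative justification of the parent trial's sample size. It names one number (84 per group) and computes on another (100 in total), and neither is the planned number of completers (112). The paragraph attributes its results to the trial's own design, does not present 100 as a conservative or sensitivity case, and does not derive it from 112, 160 or 168. A reader therefore cannot connect the stated detectable difference to the trial being run.

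The Design section also gives staff two recruitment targets. At 30% dropout, 112 completers means about 160 men, while the race-blocked randomisation is to end at 168. What is at stake is whether the justification describes the trial and whether recruitment has one target.

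**Working it through.** **Inputs, all from the documents.** Pilot changes 2.4 and 0.9; SD 1.7; two-sided alpha 0.05; 1:1 allocation; total 100 (Power Estimate). 112 completers, about 160 enrolled, 30% dropout, 84 per arm (Design).

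**Step 1: how the sample sizes connect.**
- 160 × 0.70 = 112, so the enrolment, dropout and completer figures under Setting agree.
- 2 × 84 = 168, and 168 × 0.70 = 117.6, about 118 completers (59 per arm).
- Neither route gives 100.

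**Step 2: reproduce the printed figures.**
- Pilot effect: d = (2.4 − 0.9)/1.7 = 0.88.
- Detectable d at 80% power, normal approximation: (1.960 + 0.842) × √(2/n). With n = 50 per arm this is 2.802 × 0.200 = 0.560.
- The two-sample t-test (noncentral t, 2n − 2 df) gives 0.566, and 0.566 × 1.7 = 0.96 points.
- Power at d 0.88 is 99.2%.

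The printed 0.96, 0.57 and above 99% are reproduced at 50 per arm.

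**Step 3: the same t-test at the completer numbers that the plan implies.**

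| Completers (per arm) | Detectable d, 80% power | In SPPB points (× 1.7) | Power for 0.96 points | Power for d 0.88 |
|---|---|---|---|---|
| 100 (50), as computed in the plan | 0.566 | 0.96 | 80% | 99.2% |
| 112 (56), planned completers | 0.534 | 0.91 | 84% | 99.6% |
| 118 (59), 168 at 30% dropout | 0.520 | 0.88 | 86% | 99.7% |

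The stated value differs from the value at planned completers by 0.96 − 0.91 = 0.05 points, and the stated value is the larger.

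**Step 4: how far the t-test stands in for the planned test.** The planned test has 2 df and adjusts for baseline. As an illustration, assume that the whole effect lies in one of the two contrasts and that baseline adjustment gains nothing.
- The large-sample noncentrality needed for 80% power is 9.635 on 2 df against 7.849 on 1 df, so the detectable difference grows by √(9.635/7.849) = 1.108.
- With the noncentral F at 56 per arm, the detectable d is 0.595, and 0.595 × 1.7 = 1.01 points. Power at d 0.88 is 98.9%.
- At 50 per arm, power at the pilot effect is 98.0%.
- Baseline adjustment multiplies the SD by √(1 − r²), where r is the correlation of baseline with change. The documents give no r. Assuming r = 0.3 gives 1.01 × 0.954 = 0.96 points; assuming r = 0.5 gives 1.01 × 0.866 = 0.88 points.

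**The case against.** The strongest reply is that nothing here harms the trial. Every input to the power calculation is printed and the result reproduces. Recruitment is governed by the 112-completer rule, not by the power paragraph, and a calculation at 100 is more than met by 112 on the protocol's own basis. Enrolment is only approximately 160, 168 is 5% above that, and 168 down to 112 is a loss of one third, not far from a rounded 30%. All of this stands, and it is why the point is minor. It does not supply the missing link: no text ties 100 to any planned number, and the same paragraph names 84 per group.

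A second reply also has force. A restated 0.91 would come from the same change-score t-test and so is not the power of the planned analysis. On the illustration above, the 2-df figure at 56 per arm runs from 1.01 points with no baseline gain to 0.96 or 0.88 under assumed correlations. The intention-to-treat mixed model is also not confined to completers. Hence the restated figures need a label.

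Three stronger readings are tempting and not supported:
- A reader might infer that the trial is underpowered. On the stated assumptions the t-test power at the pilot effect exceeds 99% at 100, 112 and 118 completers.
- A reader might infer that 0.96 is a miscalculation. It is correct for 50 per arm.
- A reader might infer that 0.96 is conservative, or that power exceeds 99%, for the primary analysis as planned. That is shown only for the change-score t-test; the 2-df illustration gives 98.9% at 56 per arm.

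**Conclusion.** The inconsistency holds as a minor point. The plan carries totals of 100, 112, about 160 and 168. Only 112 and 160 are linked by the stated dropout rate, and the printed power figures belong to the one total that is planned nowhere. Against 112 completers the detectable difference is overstated by 0.05 SPPB points. Against 168 randomised at 30% dropout it is overstated by 0.96 − 0.88 = 0.08 points. The two recruitment targets differ by 168 − 160 = 8 men.

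These sizes rest on a two-sample t-test of change scores with SD 1.7, two-sided 0.05, equal arms and a common endpoint. The common endpoint is itself uncertain: men enrolled after 10/1/2023 have most measures only at months 0 and 3, so not every completer contributes a month-6 SPPB. The documents do not say how many such men there will be.

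**What to change.** State one randomised number, one dropout rate and one completer number, and use them in Setting, Study Arms, the randomisation paragraph and the Power Estimate. Which set stands is for the sponsor to decide; 160, 30% and 112 is the only set that agrees with the stated dropout.

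Replace the sentence based on 100 with figures at the chosen completer number:
- 112 completers: 80% power for 0.91 points (d 0.53) and 99.6% power for d 0.88.
- 168 randomised at 30% dropout, about 118 completers: 80% power for 0.88 points (d 0.52) and 99.7% power for d 0.88.

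Label these as two-sample change-score t-test values (SD 1.7, two-sided 0.05), not as the power of the baseline-adjusted 2-df mixed-model test. Add a sentence saying that men enrolled after 10/1/2023 have most measures only at months 0 and 3, so the completer count is not the number with a month-6 SPPB.

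The cost is wording and a few restated figures. The analysis does not change, and nothing here calls for enrolment beyond what the protocol already states.
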